8.1. Primary Objectives

To describe the prescribing patterns before and after the changes to the domperidone label and distribution of a DHPC and estimate and compare the overall proportion of domperidone prescriptions before and after implementation of the risk minimisation measures regarding the following measures:

- Composite endpoint consisting of the following components:
 - Maximum daily dose;
 - Duration of use (>7 days);
 - Concomitant medications that prolong the QT-interval or are potent or strong CYP3A4 inhibitors;
 - Prescribing to patients with contraindicated conditions, e.g., moderate or severe liver disease, underlying cardiac diseases; and
 - Prescribing for off-label indications

Domperidone is used as needed, therefore the duration of use may not be the same as the number of days for which domperidone is supplied. As a result, duration of use will be assessed under the following 2 scenarios, which will be likely to bracket the actual (but unknown) situation:

- 1. Domperidone is used only for as little as 1 dose after it is prescribed, and
- 2. Domperidone is used for the entire number of days supplied.

This is intended to bracket the plausible values for duration of use

Primary test statistic: In each country studied, the change in the proportion of all prescriptions that comply with the label based on the above composite endpoint during the 12 months before the label change versus the 12 months after the label change is the primary statistic to be evaluated as a measure of the effectiveness of the label change in that country. The statistic will be evaluated as a risk ratio, i.e., as the ratio of the proportion of prescriptions that met all conditions in the composite endpoint between 1 April 2013 and 31 March 2014 and the proportion of prescriptions that met all conditions of prescriptions that met all conditions in the composite endpoint between 1 October 2014 and 30 September 2015. The point estimate and 95% confidence interval for the above risk ratio will be reported. There are several versions of the composite endpoint are implemented in the databases and the risk ratio (point estimate and 95% confidence interval) will be reported for each. Note that the term "risk ratio" is being used in the sense of a ratio of probabilities (the probability of a prescription being consistent with the new label).

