9.2. Setting and Study Population

9.2.1. Study Setting and Population

The study population will be defined as all patients receiving domperidone in the outpatient setting during the pre-defined periods (pre- and post- implementation periods of the risk minimisation activity) in the selected European Union countries (France, Germany, United Kingdom, Belgium, and Spain). Patients will be included in the study cohort if they have at least 1 prescription for domperidone in the selected databases during the pre-defined periods, and have membership or have been registered with the practice and have available medical history for at least 180 days before the domperidone prescription.

The date of the first prescription of domperidone in the pre-defined study periods will be defined as the index date. Patients will be followed from the index date to the earliest of the following dates:

- end of the study period;
- transfer out of the practice; or
- end of the practice's qualification as up to standard (a designation used in some databases to differentiate between practices that meet a data standard and those who do not for databases, such as CPRD).

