9.2.2. Study Period

The study period will be divided into a background period and pre- and post- implementation periods of risk minimisation measures as follows:

- A background period (1 January 2011 through 31 March 2013)
- A 1-year pre-implementation period of risk minimisation measures (1 April 2013 through 31 March 2014)
- A 1-year post-implementation period of risk minimisation measures (1 October 2014 through 30 September 2015)

The period during which the label change took place and the DHPC was sent will be used as the period during which the risk minimisation measures were implemented (1 April 2014 through 30 September 2014).

Because the amendments to the product information were suggested by the PhVWP in October 2011, the study will track prescribing pattern changes from 1 January 2011 (a time that preceded most of the discussion and implementation of the label changes, i.e., a background period) through 30 September 2015.

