9.5. Study Size

The study size will vary according to country and data source. All patients available in the study population will be considered for the analysis. Preliminary estimates indicate that the suggested databases capture at least several thousands of domperidone prescriptions in each of the countries being studied.

Review of domperidone sales data for 2015 from IMS and from the CPRD indicates that the number of prescriptions in each of the databases varies by country. The lowest number of prescriptions was observed in the Belgian database, where the count was 22,000.

Table 2 shows the approximate number of prescriptions for a study with the same number of prescriptions in pre-intervention period and the post-intervention to have 90% power to detect, p<0.05 (2-sided test) risk ratios from 1.1 to 1.4 according to the risk during the pre-intervention period. Note that the "risks" are the probabilities of a prescription meeting the label requirements, so a risk ratio of 1.1 represents a 10% improvement in label compliance when comparing the post-intervention period to the pre-intervention period.

Table 2:Approximate number of Subjects Required per Group (Before Intervention, After Intervention) Under Various Scenarios				
"Risk" of complying with label before	"Risk" Ratio =	"Risk" Ratio =	"Risk" Ratio =	"Risk" Ratio =
the intervention period	1.1	1.2	1.3	1.4
10%	16,000	4,500	2,000	1,200
20%	7,200	1,800	900	500
30%	4,000	1,100	500	300
40%	2,700	700	300	200
50%	1700	500	200	100
60%	1200	300	200	100
70%	700	200	100	100
80%	400	100	100	100

Thus, if compliance with the new label requirements as low as 10% in the pre-intervention period, the study will have \geq 90% power to detect even a risk ratio of 1.1 (a 10% improvement), and smaller improvements would be of limited public health interest. If compliance with the new label is higher than 10% in the pre-intervention period, the study will have \geq 90% power to detect smaller improvements in compliance with the new label. All domperidone prescriptions that are captured during the study period and meet the inclusion criteria will be included in data analysis.

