9.9. Limitations of the Research Methods

9.9.1. Strengths

- The study will use longitudinal real-life data on the utilisation of domperidone in different European countries with a pre- and post- study design to measure the effectiveness of the risk minimisation activities and examine changes on prescribing patterns. Data on prescription patterns prior to the label change provide a useful comparator for the prescription patterns observed after the label change.
- The data from this study are not collected by specific consent of patients or prescribers and thus are not subject to volunteer and reporting bias.
- All prescriptions for eligible patients that are captured by the database will be included, providing a robust sample size and a statistically-reliable estimate of compliance with the new domperidone label.
- Data on prescription patterns prior to the label change provide a useful comparator for the prescription patterns observed after the label change and distribution of the DHPC. Thus this study provides an opportunity to demonstrate not only the final outcomes of the implemented risk minimisation measures, but also to demonstrate the effectiveness of the implementation process by comparing the endpoints "before" and "after" the implementation.
- Using the combination of the prescribers' survey and healthcare database analysis, the extent of domperidone on-label vs. off-label prescription will be assessed both in terms of process indicators (investigated through survey) and outcome indicators (investigated through database analysis). This should provide a comprehensive view of the effectiveness of domperidone risk minimisation measures.

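### Practice data standard is stated only as an exit rule and the pre/post ratio is not tied to practices present in both years: a cheap improvement of unknown size

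*Protocol*

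**What the plan says.** **Entry (Protocol 9.2.1).** A patient needs at least one domperidone prescription in the defined periods and must "have membership or have been registered with the practice and have available medical history for at least 180 days before the domperidone prescription". This tests the length of the patient's record. It does not mention the practice's data standard.

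**Exit (Protocol 9.2.1).** Follow-up stops at the earliest of three events, one of which is "end of the practice's qualification as up to standard". The protocol explains this status as "a designation used in some databases to differentiate between practices that meet a data standard and those who do not for databases, such as CPRD". No equivalent is described for the IMS databases used for France, Germany, Belgium and Spain.

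**Prescriptions analysed (Protocol 9.5).** "All domperidone prescriptions that are captured during the study period and meet the inclusion criteria will be included in data analysis". No condition requires a practice to contribute to both years.

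**Primary statistic (Protocol 8.1).** For each country, the compliant proportion in April 2013 to March 2014 is compared with that in October 2014 to September 2015: "The statistic will be evaluated as a risk ratio", with a 95% confidence interval. No restriction, stratification or adjustment by practice is stated.

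**Comparability (Protocol 9.9.1).** The pre-change data are listed as a strength: "Data on prescription patterns prior to the label change provide a useful comparator for the prescription patterns observed after the label change". The limitations in 9.9.2 mention neither a change in contributing practices nor a change in recording completeness. In Annex 2, adjustment for confounding is marked not applicable (item 10.5), and the item on data-source quality issues is answered no (11.4).

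**The concern.** The protocol treats up-to-standard status as relevant, since it stops counting a patient when the practice loses it. It does not say that the practice must hold that status at the prescription or during the look-back. On the text as it stands, a practice that qualifies part-way through could supply weaker records to the first window and better ones to the second, and a practice that lapses could supply only the first.

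The endpoint is sensitive to this because it is built from what is recorded:

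- A prescription with no qualifying diagnosis is classed as unknown indication (9.3.2). It counts as on-label in versions 1 and 3 of the composite and as off-label in versions 2 and 4 (9.7).
- A contraindicated condition or co-medication that is not recorded counts as compliance in all four versions (9.3.4 to 9.3.6).

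At stake is the reading of the primary ratio as a measure of the label change. Part of any movement could come from a different set of practices or from fuller recording, and the planned output would not separate these from changed prescribing.

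**Working it through.** The protocol has no figure of its own on this point to reproduce. The only plan number used is the smallest country count, 22,000 prescriptions (Belgium, 2015 data, 9.5), applied here to each 12-month window. Turnover, compliance gap and completeness are assumptions. Ratios are post/pre, the direction used in 9.5.

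**1. Turnover.** Assume no change in prescribing and 40% compliance in continuing practices. A share w of pre-year prescriptions comes from practices absent in the post year, with compliance p_leave.

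- pre = w·p_leave + (1 − w)·0.40; post = 0.40; RR = post/pre
- half-width on the log scale = 1.96·√[(1 − pre)/(22,000·pre) + (1 − post)/(22,000·post)]

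| w | p_leave | pre | RR | log RR | half-width | 95% limits |
|---|---|---|---|---|---|---|
| 10% | 30% | 0.39 | 1.026 | 0.0253 | 0.0231 | 1.002 to 1.050 |
| 20% | 30% | 0.38 | 1.053 | 0.0513 | 0.0234 | 1.028 to 1.077 |
| 30% | 30% | 0.37 | 1.081 | 0.0780 | 0.0236 | 1.056 to 1.107 |
| 20% | 50% | 0.42 | 0.952 | −0.0488 | 0.0224 | 0.931 to 0.974 |

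**2. Dependence on independence.** These limits treat prescriptions as independent, although patients and practices contribute several each. The design effect at which the interval just reaches 1 is (log RR / half-width)². That gives about 1.2, 4.8, 10.9 and 4.7 for the four rows. The 10% case therefore excludes 1 only if there is almost no clustering.

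**3. Completeness of indication.** Let t be the true nausea/vomiting share, with all other prescriptions for listed off-label conditions. Let r be the probability that the diagnosis is recorded, and let 80% pass the other criteria.

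- Version 1 (unknown counted on-label): 0.8·[1 − (1 − t)·r]
- Version 2 (unknown counted off-label): 0.8·t·r

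With r rising from 0.5 to 0.6 and prescribing unchanged:

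- t = 0.4: version 1 goes from 0.560 to 0.512, RR 0.91; version 2 from 0.160 to 0.192, RR 1.20.
- t = 0.6: version 1 goes from 0.640 to 0.608, RR 0.95; version 2 from 0.240 to 0.288, RR 1.20.

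**4. Completeness of contraindications and co-medication.** Let v be the true violation rate and c the capture rate, so apparent compliance on this component is 1 − v·c.

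- v = 0.1, c from 0.6 to 0.7: 0.93/0.94 = 0.99
- v = 0.3, c from 0.6 to 0.7: 0.79/0.82 = 0.96

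In versions 2 and 4, steps 3 and 4 push in opposite directions. The sizes above would let the indication effect dominate, but both are assumed, so the documents do not settle the net direction.

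**The case against.** The strongest reply is that the entry gap is an inference from silence. A qualification that ends must first have been held, no text admits records from before qualification, and 9.6 leaves extraction to supplier practice. Entry flags and restricted sensitivity analyses may also sit in an analysis plan that is not shown. This stands in part: a reader might infer that sub-standard records will be used, and the protocol does not say so. It does, however, fix the entry rule, the exit rule and the inclusion of all eligible prescriptions, and on those terms the condition is absent.

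Second, the scope is narrow. Only CPRD is named as carrying the flag, so the entry/exit mismatch is explicit for one of five countries, and the 22,000 used for precision is from Belgium, where no flag is described. This stands. The lack of any tie to practices in both years applies everywhere.

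Third, the inputs are assumptions. The one panel build-up on record (Spain, Annex 5: GPs from 2011, specialists from 2012) began before the pre window opened. Annex 5 also describes CPRD validity as extensively studied. Both are fair, although general validity is not the same as equal completeness in two particular years.

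Fourth, for 10% baseline compliance, 9.5 calls improvements below a ratio of 1.1 of limited public health interest, and all four turnover ratios fall short of that. True, but a downward artefact can hide a real gain: with leavers at 50% and w = 20%, compliance rising from 40% to 44% in continuing practices gives 0.44/0.42 = 1.048 instead of 1.10.

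Fifth, the four versions, the quarterly rates, the trend in apparent indication and the component comparisons make drift visible. They do, and versions 1 and 2 moving apart would be a useful sign of changed recording. They do not separate practice turnover from changed prescribing.

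**Conclusion.** The point holds as a low-cost improvement. As written, an open set of practices with no stated entry standard feeds an endpoint that depends on recorded codes, and the primary ratio is a crude comparison of two separate years. It can therefore move without any change in prescribing. Whether it will, and by how much, the documents do not show.

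Under the assumed turnover of 10–30% and a 10-point gap around 40% compliance, the spurious ratio is about 0.95 to 1.08, against roughly ±2.3% at 22,000 independent prescriptions per year.

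Three stronger readings are tempting and not supported:

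- That the primary ratio is biased. No turnover or completeness figure is given, and no stated figure is shown to be wrong.
- That every such artefact would be statistically significant. That needs independence, and the smallest case has a lower limit of only about 1.002.
- That poorer pre-year data understate pre-year compliance in versions 2 and 4. Missed indications lower apparent compliance there, but missed contraindications raise it.

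**What to change.** **Protocol 9.2.1.** Where the database carries the flag, require the practice to be up to standard from at least 180 days before each prescription through the prescription date. Keep the existing exit rule.

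**Protocol 9.7.** Keep the all-practice risk ratio. Add, as a sensitivity analysis, the ratio for each of the four versions restricted to practices contributing throughout both 12-month windows as defined in 9.2.2. For each window report the number of practices, the number of prescriptions and the share with unknown indication.

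**Cost and limits.** One entry condition and one restricted re-run per country, with fewer prescriptions in the restricted analysis. The restriction removes practice turnover but not better recording within the same practices, which is why the unknown-indication share should accompany it. A 180-day condition does not cover the hepatic look-back to 1 January 2011 (9.3.4).

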9.2.2. Study Period

The study period will be divided into a background period and pre- and post- implementation periods of risk minimisation measures as follows:

- A background period (1 January 2011 through 31 March 2013)
- A 1-year pre-implementation period of risk minimisation measures (1 April 2013 through 31 March 2014)
- A 1-year post-implementation period of risk minimisation measures (1 October 2014 through 30 September 2015)

The period during which the label change took place and the DHPC was sent will be used as the period during which the risk minimisation measures were implemented (1 April 2014 through 30 September 2014).

Because the amendments to the product information were suggested by the PhVWP in October 2011, the study will track prescribing pattern changes from 1 January 2011 (a time that preceded most of the discussion and implementation of the label changes, i.e., a background period) through 30 September 2015.

9.3. Variables

9.3.1. Demographic Characteristics

Information on patients' age, sex, and geographic region will be extracted. Diagnoses will be extracted from a read codes (CPRD), ICD codes, or will be determined based on laboratory test results.

9.3.2. Indication

Indication will be estimated from the diagnoses recorded in the time period preceding each domperidone prescription:

- The indication for the prescription will be defined as nausea/vomiting if the subject has a recorded diagnosis classified as nausea or as vomiting, on the day of the prescription or in the preceding 7 days.
- For those prescriptions whose indication is not defined as nausea/vomiting, the indication will be defined as off-label if the subject has, in the 2 months up to and

including the date of domperidone prescription, a diagnosis classified as one of the following:

- o GERD;
- Abdominal bloating, gastric dysmotility, delayed gastric emptying;
- o IBS;
- Suppressed lactation, failed lactation, lactation not established, decreased lactation, lactation problem; or
- Orthostatic hypotension and a diagnosis of Parkinson's disease.
- For those prescriptions not classified as above, the indication will be classified as unknown.

For a list of the diagnostic terms and codes that will be used to identify the above conditions, see Annex 6.

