7.2. Background

In 2011, the EU Pharmacovigilance Working Party (PhVWP) recommended that the product information for domperidone-containing medicines should be updated to reflect the risk of adverse cardiac effects of domperidone including QT prolongation, arrhythmias, and sudden cardiac death, and that domperidone should be used with caution in patients with certain heart conditions, including heart failure, a previous heart attack, angina (chest pains), and heart rhythm disorders. In response to this recommendation, the SmPC was updated in 2012 to include QT prolongation as an adverse drug reaction (ADR).

In March 2013, the EMA PRAC initiated a review of domperidone-containing medicines at the request of the Federal Agency for Medicines and Health Products (FAMHP), under Article 31 of Directive 2001/83/EC over concerns about cardiac adverse effects of domperidone. Subsequently, PRAC recommended that the product label (Summary of Product Characteristics/SmPC and Patient Information Leaflet/PIL) of domperidone-containing medicines should be updated to strengthen the information regarding cardiac risks. In addition, PRAC raised concerns that there may be off-label use of domperidone for the stimulation of lactation in breastfeeding women, for the treatment of

gastro-oesophageal reflux disease (GERD), for the treatment of diabetic and non-diabetic gastroparesis, and for the treatment of symptoms of postural hypotension in Parkinson's patients. More recently the EMA asked that IBS be included in the present study as an off-label indication.

The recommended changes following conclusion of the Article 31 referral included the following:

- restriction of the indication to nausea and vomiting;
- limitation of duration of use to 7 days;
- reduction of the maximum daily dose to 10 mg TID for adults and adolescents (12 years of age and older and weighing 35 kg or more);
- reduction of the maximum daily dose to 0.25 mg/kg TID for neonates, infants, children (less than 12 years of age), and adolescents weighing less than 35 kg;
- contraindication of the combination with other drugs that increase the cardiac risks by themselves or increase the plasma level of domperidone; and
- contraindication in patients with moderate or severe hepatic impairment or certain cardiac conditions.

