9.7. Data Analysis

Data analysis in the study will be descriptive. Continuous variables will be presented using appropriate descriptive statistics, such as mean, median, standard deviation and range. Categorical variables will be presented using percent and frequency tables. The rates and 95% CI of all study endpoints (i.e., risk minimisation indicators) will be calculated for the 2011-2015 period, using quarterly time blocks for the pre- and post- risk minimisation implementation periods. The rates will be calculated per 1000 domperidone-treated patients or as percentage of domperidone prescriptions, as appropriate. Paediatric data will be described separately from adult patients and rate of paediatric use will be calculated as fraction of overall domperidone utilisation. Missing values will be reported as missing and no imputation will be undertaken. All data analysis will be done in SAS using the version that is current when the analyses are done.

The rates for the primary endpoints of the study (the proportion of all prescriptions that are consistent with the revised label) will be calculated 4 ways to address uncertainty about 1) Unknown indication (is it assumed to be nausea and vomiting and therefore on-label, or is it assumed to be some other indication and therefore off-label) and 2) Duration of use that may be shorter than the days' supply (prescriptions with more than 7 days' supply assumed to

be intended for ≤ 7 days use, and provision of additional tablets for possible future episodes, and therefore on-label, versus assumed to be for >7 days use and therefore off –label):

- 1. Unknown indication assumed to be nausea and vomiting. Duration assumed to be ≤ 7 days (most optimistic scenario) meets the following conditions:
 - a. Prescription for nausea and vomiting or unknown indication but no recent diagnosis of GERD, gastroparesis, IBS, symptoms of postural hypotension in Parkinson patients, or as an aid to lactation;
 - b. Dose no higher than recommended;
 - c. No prescription to patients with certain cardiac and hepatic conditions; and
 - d. No co-prescription with CYP3A4 inhibitors or QT-prolonging drugs. (This considers such contraindicated co-medications only when they were prescribed ≤ the date of the domperidone prescription.)
- 2. Unknown indication assumed to be an off-label indication, duration assumed to be \leq 7days (an intermediate scenario) meets the following conditions:

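### The 2-month window in section 9.3.2 also covers the Parkinson's diagnosis, so off-label use for postural hypotension in Parkinson's patients may be under-counted, by an amount the protocol leaves open

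*Protocol*

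**What the plan says.** Protocol section 9.3.2 classifies each prescription in three steps.

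1. Nausea/vomiting, if such a diagnosis is recorded on the day or in the preceding 7 days.
2. Off-label, if step 1 does not apply and a listed diagnosis falls "in the 2 months up to and" including the prescription date. This one lead-in governs every item on the list. The list ends with "Orthostatic hypotension and a diagnosis of Parkinson's disease", the only item that needs two diagnoses. No separate look-back is given for Parkinson's disease.
3. "For those prescriptions not classified as above, the indication will be classified as unknown".

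Section 9.7 words the same criterion differently. A compliant prescription has "no recent diagnosis of GERD, gastroparesis, IBS, symptoms of postural hypotension in Parkinson patients, or as an aid to lactation". There, Parkinson's describes the patient, and recency seems to attach to the hypotension.

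Section 7.2 records why the item is in the study: the PRAC was concerned about off-label use, among others "for the treatment of symptoms of postural hypotension in Parkinson's patients".

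**The concern.** A short window makes sense for a complaint that may be the reason for today's prescription. Parkinson's disease is not that complaint. It identifies the patient in whom postural hypotension is being treated, and it is lifelong whether or not the practice has coded it lately. Requiring a recent code for it can only reduce detection of this use.

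The protocol treats another lasting disease differently. Section 9.3.4 looks for the hepatic contraindication back to 1 January 2011.

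Two outputs are at stake:

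- **Indication.** Apparent indication is tabulated (9.7) and its time trend is a secondary objective (8.2). A missed prescription appears there as unknown and cannot be recovered as Parkinson's-related use.
- **Composite.** Versions 1 and 3 treat an unknown indication as on-label.

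The two wordings are a problem in themselves. Section 9.6 leaves extraction and analysis to the standard practices of the data suppliers, so one rule could be programmed in two ways across the five countries.

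**Working it through.** The protocol states no figure for this rule, so there is none to reproduce. The check is a reading of the text, followed by an illustration on assumed rates.

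**Step 1: one patient under each reading.** Take a prescription with orthostatic hypotension coded within 2 months, Parkinson's disease last coded 3 months ago, no nausea/vomiting code within 7 days and no other listed off-label diagnosis.

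| Reading | Class | Indication in versions 1 and 3 | Indication in versions 2 and 4 |
|---|---|---|---|
| 9.3.2 taken literally | unknown | on-label | off-label |
| Parkinson's as patient status | off-label | off-label | off-label |

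The readings differ in the indication tabulation and in versions 1 and 3 only. In those versions the prescription counts as compliant only if it also meets every other condition. A nausea/vomiting code within 7 days, or another listed off-label diagnosis, would settle the class under 9.3.2 whatever the Parkinson's code.

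**Step 2: how many could be lost.** Assume Parkinson's disease is coded at random r times per patient-year (Poisson). The chance of no code in a window of w years is exp(−r·w). For 2 months, w = 2/12. For comparison, the 180 days of history required by 9.2.1 give w = 180/365.

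| r per year (assumed) | Captured, 2 months | Missed, 2 months | Missed, 180 days |
|---|---|---|---|
| 0.5 | 8.0% | 92.0% | 78% |
| 1 | 15.4% | 84.6% | 61% |
| 2 | 28.3% | 71.7% | 37% |
| 4 | 48.7% | 51.3% | 14% |
| 6 | 63.2% | 36.8% | 5% |
| 12 | 86.5% | 13.5% | 0.3% |

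More than half is missed at 2 months only if exp(−r/6) > 0.5, that is r < 6·ln 2 = 4.16 codings a year.

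**Step 3: effect on the primary risk ratio, versions 1 and 3.** Assume true compliance of 50% before and 55% after, a ratio of 1.10. Let the missed but otherwise compliant prescriptions be the same share of all prescriptions in both periods.

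- Share 1%: (0.55 + 0.01)/(0.50 + 0.01) = 1.098.
- Share 5%: (0.55 + 0.05)/(0.50 + 0.05) = 1.091.

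Both shares are assumptions. The effect on the ratio is small, so the harm falls mainly on the estimate of this particular use.

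**Step 4: would an unlimited look-back be neutral?** Annex 5 says Spanish general-practice data start in 2011. If that means 1 January 2011, the longest possible history is 27 to 39 months for prescriptions in the pre-implementation year (1 April 2013 to 31 March 2014). For the post-implementation year (1 October 2014 to 30 September 2015) it is 45 to 57 months. Spanish specialist data start later, in 2012. An any-time rule would therefore find more Parkinson's codes after implementation than before, for reasons unrelated to prescribing.

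**The case against.** The literal reading is not the only one. The last list item can be taken as hypotension in the window plus Parkinson's as a status, and 9.7 leans that way. This stands, but it argues for an amendment: if status was intended, 9.3.2 should say so.

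A reader might infer that this use will be largely missed. The documents do not support that, because no re-coding rate is given and the range in the working is wide. Random coding is also doubtful. These patients have a hypotension code and a domperidone prescription within the same 2 months, so they were recently seen, and several of the databases record during office visits. Capture could exceed the figures shown.

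The protocol already limits the consequence. Versions 2 and 4 count every unknown as off-label, all versions are reported, and 9.9.2 discloses that indication is deduced from diagnoses recorded on or shortly before the prescription. This stands for the composite. It does not restore the Parkinson's row of the indication table.

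A reader might also infer that a longer Parkinson's look-back costs nothing in specificity. It does cost something. Annex 6 counts syncope and collapse (780.2) and heat syncope (992.1) as orthostatic hypotension, and secondary parkinsonism (332.1) as Parkinson's. A recent faint in a patient with an old parkinsonism code could be labelled off-label when domperidone was given for uncoded nausea.

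Finally, a reader might extend the point to GERD and gastroparesis. Those diagnoses are themselves the presumed indication. Two months is a design choice for them that contradicts nothing in the protocol, and a different length would be a preference.

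**Conclusion.** The point holds in limited form. On its literal text, 9.3.2 requires a Parkinson's code within 2 months of the prescription, and 9.7 does not clearly require the same. Followed as written, the rule can only lower detection of an off-label use that the PRAC named.

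The loss through this requirement alone is about 92% to about 14% for assumed rates of 0.5 to 12 codings a year, under random coding. The true value cannot be had from the documents, so the supportable claim is that this use may be under-counted. The effect is confined to the indication tabulation and time trend and to composite versions 1 and 3. Under the order of classification in 9.3.2, versions 2 and 4 do not change. The point merits an amendment before extraction but does not threaten the primary comparison.

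**What to change.** Amend 9.3.2 as follows and bring the wording of 9.7 into line:

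- Keep the 2-month window for orthostatic hypotension.
- Give Parkinson's disease its own longer look-back, of the same fixed length before each prescription in the pre- and post-implementation periods. It should be at least the 180 days that eligibility guarantees in 9.2.1.
- Run all available history for Parkinson's disease as a sensitivity analysis. At low coding rates even 180 days would miss many patients.

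The cost is one changed look-back rule and one extra run on data already held. There are two downsides to state in the protocol. A few recent syncope codes in patients with an older parkinsonism code may be labelled off-label. In the all-history run, detection may rise over calendar time as records lengthen, so its pre/post change should not be read as a change in prescribing.
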